### 4.3. PHARMACOKINETIC ENDPOINTS

Pharmacokinetic analysis of plasma (for all compounds) and urine (for AZD9150 only) concentration data for AZD9150, AZD5069 and its metabolite AZ13587715, treme and MEDI4736 will be performed by  on behalf of AstraZeneca. The actual sampling times will be used in the parameter calculations and PK parameters will be derived using non-compartmental methods. As data permit, the following parameters will be determined for each analyte:

## Statistical Analysis Plan

### Pharmacokinetic parameters for AZD5069 and AZ13587715:

- Single dose:  $C_{max}$ ,  $T_{max}$ , AUC,  $AUC_{(0-t)}$ ,  $AUC_{(0-8)}$ ,  $AUC_{(0-10)}$ ,  $AUC_{(0-12)}$ , apparent plasma clearance (CL/F) (AZD5069 only), apparent volume of distribution ( $V_z/F$ ) (AZD5069 only), MRT (AZD5069 only), and  $t_{1/2}$
- Multiple dose:  $C_{ss\ max}$ ,  $T_{ss\ max}$ ,  $C_{trough}$ ,  $AUC_{(0-t)}$ ,  $AUC_{(0-8)}$ ,  $AUC_{(0-10)}$ ,  $AUC_{(0-12)}$ ,  $V_z/F$ , apparent plasma clearance at steady state (CL/F),  $R_{ac}$
- Metabolite-to-parent ratio (MR) will be calculated after single and multiple doses

### Pharmacokinetic parameters for MEDI4736/treme:

- $C_{max}$ ,  $T_{max}$ ,  $C_{trough}$ , and Concentration at the end of infusion ( $C_{EOI}$ ).

Where possible the terminal elimination rate constant ( $\lambda_z$ ) will be calculated by log-linear regression of the terminal portion of the concentration-time profiles where there are sufficient data and the terminal (elimination) half-life ( $t_{1/2\lambda_z}$ ) will be calculated as  $\ln 2/\lambda_z$ . The  $AUC_{(0-t)}$  and additional partial AUC values will be calculated using the linear up, log down trapezoidal rule. Where appropriate, the  $AUC_{(0-t)}$  will be extrapolated to infinity using  $\lambda_z$  to obtain AUC. The area under the concentration-time curve across the dosing interval,  $AUC_{(0-\tau)}$  will be calculated using the linear up, log down trapezoidal rule. The CL/F following single dose or multiple dosing will be determined from the ratio of dose/AUC or dose/ $AUC_{(0-\tau)}$ , respectively. The volume of distribution ( $V_z$ ) following single or multiple dosing will be determined as dose/ $(\lambda_z * AUC)$  or dose/ $(\lambda_z * AUC_{(0-\tau)})$ , respectively. The accumulation ratio (RAC) will be calculated as the ratio of the appropriate partial AUC following single dose to the same partial AUC following multiple dosing. The time dependency (TCP) of the PK on multiple dosing will be assessed by the calculation of the ratio of  $AUC_{(0-\tau)}/AUC(\text{single dose})$ .

#### 4.4. PHARMACODYNAMIC ENDPOINTS

The pharmacodynamic endpoints for dose-escalation Part A include the following:

- For AZD9150: Signal transducer and activator of transcription 3 (STAT3) knockdown in blood
- For MEDI4736: Soluble programmed cell death-ligand 1 (sPD-L1)
- For AZD5069: Circulating myeloid-derived suppressor cells (MDSCs)

## Statistical Analysis Plan

In addition to the above pharmacodynamic endpoints, the dose expansion Part B also includes:

- For AZD9150: STAT3 knockdown in tumour issue
- For MEDI4736: Tumour PD-L1 expression

### **4.5. PRIMARY SAFETY ENDPOINTS**

#### **4.5.1. Dose-escalation and Safety cohorts Part A**

The primary safety endpoints for Part A include:

- Maximum-tolerated dose (MTD) based on patients who completed the DLT evaluation
- AEs, SAE, laboratory evaluations, vital signs, and physical examinations
- Treatment-emergent AEs (TEAEs), SAEs and deaths, graded in accordance with National Cancer Institute Common Terminology Criteria for Adverse Events (NCI CTCAE) v4.03.

#### **4.5.2. Dose-expansion Part B**

There are no primary safety endpoints for Part B.

### **4.6. SECONDARY SAFETY ENDPOINTS**

The secondary safety endpoints for Part A and Part B include:

- Anti-drug antibodies (ADAs)
- AEs, SAEs, laboratory evaluations, vital signs, and physical examinations
- TEAEs, SAEs and deaths, graded in accordance with NCI CTCAE version 4.03

## Statistical Analysis Plan

### 4.7. OTHER ENDPOINTS

#### 4.7.1. Blood-borne Biomarkers

Blood-borne biomarkers that may correlate with treatment or clinical response may include, but are not limited to, gene expression changes, immunogenomics (genetics associated with immune responses such as homozygosity/heterozygosity of MHC-I genes), T-cell activation or proliferation markers, T-cell repertoire changes, cytokines, CXC chemokine receptor-2 ligands, interleukin 8, and growth-regulated oncogene-alpha.

#### 4.7.2. Tumour-based Biomarkers

Tumour-based biomarkers in archival tumours that may correlate with treatment or prospectively identify patients likely to respond to treatment may include PD-L1 expression, phospho- or total STAT 3 expression, tumour genetics, immunogenomics (genetics associated with immune responses such as homozygosity/heterozygosity of MHC-I genes), characterization of immune infiltrates, gene expression or other stratification markers.

#### 4.7.3. Pharmacogenetics

Saliva samples intended for subsequent DNA analysis will be collected if a patient agrees to participate in this aspect of the study.

## Statistical Analysis Plan

### 5. ANALYSIS SETS

The analysis of data will be based on different subsets according to the purpose of the analysis. Throughout the safety results sections, erroneously treated patients (eg, patients who were assigned to dose X but received dose Y) will be accounted for based on the actual dose received.

Definition of the analysis sets used in this study are presented in Table 2 below.

**Table 2. Definition of Analysis Populations**

| Analysis Set    | Definition  |
|------------------------|--|
| All Patients           | All patients who provided written informed consent (i.e., including screen failures)   |
| Full Analysis          | All patients who were either assigned or randomized to study.  |
| Safety                 | All patients who received at least 1 dose of AZD9150, AZD5069, or MEDI4736.  |
| Pharmacokinetics (PK)  | All dosed patients with reportable AZD9150, AZD5069, treme or MEDI4736 plasma concentrations except for important protocol deviation. The important protocol deviations will be determined by the clinical team during the Blind Data Review Meeting (BRDM) planned to take place just prior to the final Database Lock (DBL). |
| Pharmacodynamics (PDN) | All patients who provided biological samples for pharmacodynamic research except for important protocol deviation. The important protocol deviations will be determined by the clinical team during the Blind Data Review Meeting (BRDM) planned to take place just prior to the final Database Lock (DBL).                    |

## Statistical Analysis Plan

| Analysis Set | Definition  |
|--------------|---|
| Efficacy     | 
All patients with unidimensional measurable disease at baseline as per the RECIST version 1.1 criteria who received at least 1 dose of study treatment (Part A) <del>barring</del> except for important protocol deviation. All patients with unidimensional measurable disease at baseline as per the RECIST version 1.1 criteria who were randomized to study treatment and received at least 1 dose of study treatment (Part B) except for important protocol deviation. Patients who have been manually assigned to treatment in Part B will be excluded from this analysis set.
 
The important protocol deviations will be determined by the clinical team during the Blind Data Review Meeting (BRDM) planned to take place just prior to the final Database Lock (DBL).
 |

While the definitions of several of the various analysis sets apply to both Part A and to Part B of the study, the data for patients from Part A and Part B will be summarized separately.

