##### 3.1.2. Dose-expansion Part B

The primary objectives of the dose-expansion phase are to:

- Evaluate the objective response rate (ORR) of AZD9150 and AZD5069 both as monotherapy and in combination with MEDI4736 in the second-line treatment of patients with RM-SCCHN and in patients with no prior exposure to anti-PD-(L)1 therapies and also in patients who have not received prior systemic treatment for RM-SCCHN (1L RM SCCHN)
- Evaluate ORR of AZD9150 as a fixed dosed Q2W in patients with no prior exposure to anti-PD-(L)1 therapies and who have not received prior systemic treatment for recurrent or metastatic SCCHN (1L RM SCCHN).

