### 3.4.2. Dose-expansion Part B

When the maximum or recommended doses for dose-expansion was established in Part A from arms A1 and A2, in parallel with the other arms of Part A, Part B of the study commenced in patients with RM SCCHN). If the RP2D combination is established earlier in one arm of Part A than the other, the Sponsor may manually assign patients to the pretreated arms (B1/B2) for the determined RP2D combination to obtain safety data (for US sites only). These manually randomized patients will not be included in any efficacy analyses and could be replaced with actual randomized patients when the RP2D for both arms is achieved.

The primary objective of the dose-expansion phase is to evaluate the objective response rate (ORR) of AZD9150 and AZD5069 both as monotherapy and in combination with MEDI4736 for treatment of patients with RM-SCCHN.

In the dose-expansion Part B (B1-B6), 10-55 eligible and efficacy evaluable second line+ patients with RM SCCHN patients were planned to be enrolled and randomized depending on the treatment Arms. In addition, non randomized Arms B7 and B8 will each enroll 48 efficacy evaluable first line SCCHN patients (no prior systemic treatment for RM SCCHN). Based on the patient's history of treatment with an anti-PD-(L)1 antibody, the

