## Statistical Analysis Plan

of responses is 35%. . The probability of observing  $\geq 15$  responses (CR or PR) out of 48 patients is 20%, given the true probability of responses is 25%. In addition, B8 will incorporate predictive power monitoring for futility beginning with the 15th patient. If at any time from the 15th patient through the 48th patient, the chance to observe 13 responses in 48 patients falls below 20%, then the arm will be stopped.

Recruitment will continue while predictive probability is measured. If an arm is stopped, no new patients will be recruited, but patients who are already on study will continue in accordance with study guidelines.

If at least 2 CRs or PRs are observed in the first 20 patients in either of the 2 pretreated expansion arms, an additional 25 to 32 patients may be enrolled to that particular pretreated combination arm.

In addition, Arms B7 and B8 each will enroll up to 48 patients who have not received any PD-L1 therapies and have received no prior systemic treatment for RM SCCHN, and will receive combination treatment of AZD9150 in combination with MEDI4736.

An efficacy evaluable patient is defined as a patient with unidimensional measurable at baseline as per the RECIST version 1.1 criteria who received at least 1 dose of study treatment. Measurable disease is defined as having at least 1 lesion that can be accurately measured in a at least 1 dimension with a minimum size of 10 mm by CT scan, except lymph nodes which must have a minimum short axis size of 15 mm.

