### 6.1.1. Presentation of Data by Treatment Group

Data will be summarized separately for each of the 2 treatment combinations (AZD9150/MEDI4736, and AZD5069/MEDI4736) in Part A. Each treatment combination will be presented in separated pages of one table.

IO Naïve 1st Line Combo, consisting of 10 identified B3 patients and all B7 patients, and IO Naïve 2nd Line+ Combo Population, consisting of all B3 subjects not in the previous group will be included in all summaries and analyses and will be presented as any treatment group is presented.

Patients who have a dose modification during the trial will be presented according to the dose group to which they were initially assigned.

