#### **8.2.2. Dose-expansion Part B - Objective Response Rate (ORR)**

The primary efficacy endpoint for dose-expansion Part B is the objective response rate (ORR). BoR as derived according to Section 8.1 (above) is the primary efficacy variable. Investigator assessed BoR will also be listed.

ORR will be calculated as the percentage of patients in the Efficacy set who have at least one confirmed overall tumour response of CR or PR before any evidence of progression, as defined by RECIST version 1.1. Confirmation of response is made by using 2 consecutive assessments that are at least 4 weeks apart. In the case where a patient has 2 non-consecutive overall visit responses of PR, then, as long as the time between the 2 visits of PR is greater than 4 weeks and there is no PD between the PR visits, the patient will be defined as a responder (PR). Similarly, if a patient has overall visit responses of CR, NE, CR, as long as the time between the 2 visits of CR is greater than 4 weeks, then a best response of CR will be assigned.

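### SAP Table 2 admits only randomised Part B patients to the Efficacy set; as worded this leaves out non-randomised Arms B7 and B8 (very probably a drafting error) and directly assigned B1 patients, and the restriction is not declared

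*SAP*

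**What the plan says.** SAP Section 5, Table 2, defines the Efficacy set separately for the two parts. Part A needs measurable disease and at least one dose. Part B adds a condition: patients "who were randomized to study treatment and received at least 1 dose of study treatment (Part B) except for important protocol deviation". A further sentence removes Part B patients who were manually assigned to treatment, without naming arms. The Full Analysis row of the same table uses a wider term: "All patients who were either assigned or randomized to study".

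The set governs the primary endpoint. SAP Section 8.2.2 states "ORR will be calculated as the percentage of patients in the Efficacy set", and Section 8 applies the Efficacy set to all efficacy data.

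On allocation, SAP Section 3.4.2 states "In addition, non randomized Arms B7 and B8 will each enroll 48 efficacy evaluable first line SCCHN patients". Protocol Sections 3.5, 4.2.1 and 4.2.2 also call both arms non-randomised. Protocol Section 4.2.2 and SAP Section 3.4.2 send pretreated patients whom the investigator rules out for AZD5069 directly to B1; only the AZD5069-eligible pretreated patients go through the 1:1 web-based randomisation to B1 or B2.

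One of the two Part B primary objectives in SAP Section 3.1.2 is "Evaluate ORR of AZD9150 as a fixed dosed Q2W in patients with no prior exposure to anti-PD-(L)1 therapies", in first-line patients. That is Arm B8. The other objective also covers patients with no prior systemic treatment for recurrent or metastatic disease.

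**The concern.** A definition of an analysis set is operative text: it is what gets programmed. Followed to the letter, Table 2 leaves B7 and B8 with nobody in the ORR denominator, so two stated primary objectives would have no result. It also drops part of B1.

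The protocol's own efficacy set (Section 8.3.1 and Table 15) asks only for measurable disease and one dose. The randomisation condition is therefore a narrowing. SAP Section 13, which lists changes from the protocol, mentions only the added exception for important protocol deviations.

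The study is open-label, and B8 responses are monitored from the 15th patient. If the denominator is settled during programming, it is settled with responses already visible.

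**Working it through.** **Who meets the randomisation condition, arm by arm** (allocation rules from protocol Section 4.2.2 and SAP Section 3.4.2):

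| Arm | Route | Meets Table 2 as worded |
|---|---|---|
| B1 | 1:1 randomisation if AZD5069-eligible, otherwise direct assignment | Only the randomised part |
| B2 | 1:1 randomisation | Yes |
| B3, B5 | 2:1 or 2:2:1:1 randomisation | Yes |
| B4, B6 | 2:2:1:1 randomisation | Yes |
| B7, B8 | Non-randomised | None |

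The literal ORR denominators are therefore 0 for B7 and 0 for B8. B1 loses an unknown number.

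**What the SAP's own sizing presupposes.** For B7 and B8, SAP Section 3.6.2 gives two probabilities with about 48 patients per arm. With X ~ Binomial(48, p):

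- P(X ≤ 12) at p = 0.35 is 0.0943; the SAP states 9%.
- P(X ≥ 15) at p = 0.25 is 0.1999; the SAP states 20%.

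Both reproduce. (The protocol words the first event as fewer than 12 responses, which gives 0.051. That is a separate wording matter.) The figures make sense only if about 48 patients in each arm count towards ORR.

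**What the planned output looks like once the arms are in the set.** Exact two-sided 80% Clopper-Pearson intervals at n = 48:

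- 12 responses: 25.0% (16.9% to 34.8%)
- 13 responses: 27.1% (18.7% to 37.0%)
- 15 responses: 31.3% (22.4% to 41.4%)

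With a denominator of 0 none of these can be computed.

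**Other SAP text that conflicts with the literal rule.**

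- Section 3.6.2 monitors B8 on response counts: "If at any time from the 15th patient through the 48th patient, the chance to observe 13 responses in 48 patients falls below 20" per cent, the arm stops.
- Section 6.1.1 creates a first-line group "consisting of 10 identified B3 patients and all B7 patients" and includes it in all summaries and analyses. This brings back B7 but does not mention B8.
- Section 6.2 defines an efficacy evaluable patient with no randomisation condition.

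**The manual-assignment sentence.** SAP Section 3.4.2 explains its origin. The sponsor could place patients in B1 or B2 early to gather safety data, and "These manually randomized patients will not be included in any efficacy analyses and could be replaced with actual randomized patients". Protocol Section 4.2.2 reports one such patient, in B1. Table 2 does not carry over the limit to these placements.

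**Two smaller, separate items in the same area.**

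1. OS-12 is listed under the Efficacy set in SAP Table 3, and Section 8 puts all efficacy data there, but Section 8.3.9 uses the Safety set. The Safety set would readmit a dosed manual placement, which Section 3.4.2 bars from efficacy analyses.
2. SAP Sections 4.2.2 and 8.3.7 to 8.3.10 start the Part B clocks at randomisation for PFS, OS, OS-12 and time to first response. Protocol Section 2.2 also says randomisation for PFS and OS, while protocol Section 8.9 starts both at Cycle 1 Day 1. For non-randomised patients a randomisation date is undefined in the text.

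**The case against.** The best reply is that nobody would apply the rule literally to B7 and B8. The protocol often uses randomised as shorthand for Part B: Section 4.2.2 speaks of random assignment to B8, Section 5.7 lists B7 and B8 among arms randomised to MEDI4736, and Sections 8.2.2 and 8.10 count eight randomised arms. The SAP's objectives, sizing, monitoring and Section 6.1.1 all plan efficacy results for these arms. The table mock-ups, which might show the arm columns, are in a separate document that is not available here. This largely stands, and it rules out one tempting inference: that the sponsor means to leave B7 and B8 out of the primary analysis. The documents do not support that.

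It can also be said that manual assignment has only one natural meaning in the SAP, and that the protocol already keeps that patient out of efficacy analyses. That stands too, and it may explain why the word randomized entered Table 2. An efficacy evaluable patient, used for monitoring and replacement, also need not be the same as a member of an analysis set.

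What the reply does not reach is B1. There the documents distinguish direct assignment from randomisation within a single arm, so a programmer could reasonably apply the randomised-only rule. Monitoring of B1 would then have counted patients whom the final ORR omits. Nor does loose usage in the protocol settle Table 2, because its own Full Analysis row treats assigned and randomized as different things.

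A reader might also add 48 and 48 and quote the sum as a share of all Part B patients. The documents do not support such a figure. ORR is reported by treatment group with no pooled Part B estimate, and the share would mix planned B7/B8 numbers with the B1-B6 patients already enrolled. The planned numbers themselves vary: 48 each, up to 48 each, at least 48 each, or about 48 in total. Nor does the 15th-patient look give a lower bound for B8, since recruitment continues while predictive power is calculated.

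**Conclusion.** The wording is wrong and should be corrected before database lock. For B7 and B8 it is very probably a drafting error: on the reading the rest of the SAP implies, no patient in those arms is lost, and the defect is an undeclared conflict between Table 2, other SAP sections and the protocol's efficacy set. For AZD5069-ineligible patients assigned directly to B1, the intended reading is unclear and the B1 ORR could change. The size of that change cannot be computed, because the documents do not give their number.

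The results at stake are per-arm descriptive ORRs with 80% intervals. SAP Section 8 plans no between-group inference, so no error rate is affected. The B7/B8 sizing figures are sound at 48 per arm. The OS-12 set label is a small inconsistency, with one manual placement reported. The start-date conflict is partly the protocol's own.

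**What to change.** **Main change, SAP Table 2, Part B Efficacy.** Replace the randomised-only condition with *assigned or randomized to study treatment*, in line with the Full Analysis row. Keep the one-dose requirement and the exception for important protocol deviations. In the same edit, limit the manual-assignment exclusion to patients the sponsor placed in B1 or B2 for safety data before both recommended doses were established. The two edits belong together, because an open-ended exclusion could otherwise be read against the newly admitted assigned patients. Record the exclusion in SAP Section 13.

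**Separate minor items.** Name one analysis set for OS-12 in Table 3, Section 8 and Section 8.3.9, and keep the manual placement out whichever set is chosen. Reconcile the Part B start date for PFS, OS, OS-12 and time to first response across protocol Sections 2.2 and 8.9 and SAP Sections 4.2.2 and 8.3.7 to 8.3.10, so that it is defined for non-randomised patients. The choice of date is the sponsor's; the documents do not say which allocation dates were recorded for B7 and B8.

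**Cost.** One phrase, one limiting clause and one Section 13 entry for the main change; a line or two for each minor item. The main change needs no new data.

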8.3.1 Efficacy analysis set

All patients with unidimensional measurable disease at baseline as per the RECIST 1.1 criteria who received at least 1 dose of study treatment.

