### 3.7. TREATMENT ASSIGNMENT & BLINDING

Both Parts A and B of this study are open-label. Ideal body weight (IBW) will be used to calculate the administered dose in all arms where AZD9150 is to be infused except Arm B8 where fixed dosed AZD9150 is to be administered, i.e., 200 mg as lead-in doses on Days -7, -5, and -3 and 400 mg Q2W thereafter in a 28-day cycle. Ideal body weight will be determined using the Devine formula ([Pai and Paloucek 2000](#); see Section 7.2.1 of final study protocol). If the actual weight is less than the IBW or the patient is less than 5 feet tall, the actual weight will be used to determine the dose.

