**Table 3. Summary of Outcome Populations and Analysis Sets**

| Outcome variable                    | Populations                 |
|--|------------------------------------|
| Efficacy data                       |                                    |
| Disposition                                | All Patients, Full analysis |
| Demography                                 | Safety                      |
| OR*, disease control, DOR*, PFS, OS, OS-12 | Efficacy                    |
| Safety data                         |                                    |
| Relevant Medical History                   | Safety                      |
| Current Medical Condition at Entry         | Safety                      |
| Exposure                                   | Safety                      |
| Adverse events (including SAEs and DLTs)   | Safety                      |
| Laboratory measurements                    | Safety                      |
| Vital signs                                | Safety                      |
| Physical examinations                      | Safety                      |
| ECGs                                       | Safety                      |
| Pharmacokinetic data                | Pharmacokinetic             |
| Pharmacodynamic data                | Pharmacodynamic             |

\* Patients who are evaluable for the analysis of OR and DOR are those with measurable disease at baseline

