#### **7.2. PROTOCOL DEVIATIONS**

Protocol deviations will be captured in eCRF. These protocol deviations are classified into the following categories: prohibited use of concomitant medications, dosing, enrollment, laboratory, non-compliance, visit schedule and other. Important deviations that may affect PK, PDN, Safety, and Efficacy analyses will also be identified and used to exclude patients from their respective Analysis Sets.

All protocol deviations will be summarized by category and treatment group. All protocol deviations will be listed.

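### The final ORR is planned only after removing patients for important protocol deviations, a term with no objective criteria that is settled just before lock in an open-label trial

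*SAP*

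**What the plan says.** Protocol Section 8.3.1 (and Table 15) defines the Efficacy set as "All patients with unidimensional measurable disease at baseline as per the RECIST 1.1 criteria who received at least 1 dose of study treatment". It has no exclusion for deviations.

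SAP Section 5, Table 2 changes this. For Part B the set is limited to patients with measurable disease "who were randomized to study treatment and received at least 1 dose of study treatment (Part B) except for important protocol deviation". The same exclusion applies to Part A. On who decides, the table says "The important protocol deviations will be determined by the clinical team during the Blind Data Review Meeting (BRDM"), and it places that meeting just ahead of final database lock. SAP Section 13 lists the change as a departure from the protocol and gives no reason for it.

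SAP Section 7.2 groups deviations into categories (concomitant medication, dosing, enrolment, laboratory, non-compliance, visit schedule, other) and then states: "Important deviations that may affect PK, PDN, Safety, and Efficacy analyses will also be identified and used to exclude patients from their respective Analysis Sets".

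On the primary endpoint, SAP Section 8.2.2 says "ORR will be calculated as the percentage of patients in the Efficacy set". SAP Section 8 puts all efficacy data on that set, and Table 3 assigns objective response to it, with the footnote "Patients who are evaluable for the analysis of OR and DOR are those with measurable disease at baseline". On blinding, SAP Section 3.7 says "Both Parts A and B of this study are open-label"; protocol Section 3.6 agrees.

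**The concern.** In an open-label trial with site-assessed scans, the people judging deviations may already know who responded. Calling the review blind does not change that, and the SAP does not say which data the meeting will see. Because no rule fixes beforehand which deviations count as important, the denominator of the primary endpoint, and the responders within it, could be settled with the outcome in view.

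Each arm's result is a single ORR with an 80% interval and no comparison between groups (SAP Section 8). If removal depends on response, both the estimate and its interval are biased. SAP Section 7.1 shows how many patients were removed in each arm and lists the reasons. A reader would not see how the ORR moved without rebuilding it from listings.

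**Working it through.** **1. Is there a final ORR without the exclusion?**

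- SAP Sections 5 (Table 3), 8 and 8.2.2 all use the Efficacy set.
- The planned sensitivity analyses concern duration of response (SAP 8.3.3) and survival follow-up (SAP 11.10.3).
- The Full Analysis set serves disposition and the listing of exclusions (SAP Section 5, Table 3; Section 7.1).

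So no final ORR on the protocol's set is planned.

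**2. What does the exclusion not reach?**

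- Predictive-probability monitoring and the B3/B4 interim analysis count efficacy evaluable patients, which the SAP defines without the exclusion (Sections 3.6.2, 6.2 and 12).
- The B1/B2 expansion rule counts responses in the first 20 patients (SAP 3.6.2).
- OS-12 is unclear: Table 3 assigns it to Efficacy, Section 8.3.9 to Safety. The two must be reconciled.

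**3. The plan's nearest own figure.** Neither document gives a number of exclusions. For B7/B8, protocol Section 8.2.2 gives a 20% chance of at least 15 responses in 48 at a true rate of 25%. The exact binomial gives P(X ≥ 15 | n = 48, p = 0.25) = 0.1999, so the figure reproduces.

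As a worst case, suppose 4 patients are removed and all are non-responders. Then 14/44 = 31.8% already exceeds 15/48 = 31.25%, and P(X ≥ 14 | 48, 0.25) = 0.301. With 1 to 3 such removals, 15 responses are still needed and the chance stays at 20.0%. If 4 patients are removed without regard to response, the chance is P(X ≥ 14 | 44, 0.25) = 0.190. The rise to 30.1% therefore comes from removal that depends on the outcome, not from the smaller denominator alone.

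**4. Size of the shift in ORR.** With r responders in n patients and k removed:

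- all non-responders: r/(n − k), a shift of +(r/n) × k/(n − k)
- all responders: (r − k)/(n − k), a shift of −((n − r)/n) × k/(n − k)

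I take k = 1 to 4 as an assumption. The base is 13/48, the B8 monitoring target, with Clopper-Pearson 80% intervals: 27.1% (18.7 to 37.0).

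| k | Non-responders removed | Responders removed |
|---|---|---|
| 1 | 13/47 = 27.7% (19.1 to 37.7) | 12/47 = 25.5% (17.3 to 35.5) |
| 2 | 13/46 = 28.3% (19.6 to 38.5) | 11/46 = 23.9% (15.8 to 33.9) |
| 3 | 13/45 = 28.9% (20.0 to 39.3) | 10/45 = 22.2% (14.3 to 32.2) |
| 4 | 13/44 = 29.5% (20.5 to 40.1) | 9/44 = 20.5% (12.7 to 30.4) |

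At the B3/B4 target, 8/35 = 22.9% (13.8 to 34.5). Removing 1 to 4 non-responders gives 23.5%, 24.2%, 25.0% and 25.8%. Removing 1 to 4 responders gives 20.6%, 18.2%, 15.6% and 12.9%.

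**5. The Safety set.** SAP Table 2 defines it as "All patients who received at least 1 dose of AZD9150, AZD5069, or MEDI4736", with no deviation exclusion, and Section 13 limits the change to the PK, PD and Efficacy sets. Section 7.2 nevertheless names Safety among the sets from which patients are removed. These passages contradict each other.

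**The case against.** The strongest reply is that the exclusion is not wholly new. Protocol Section 7.7.8 already requires an efficacy evaluable patient to meet all eligibility criteria, and bases Part B on such patients. This stands for ineligible patients. It does not cover dosing, visit-schedule or other deviations, all of which SAP Section 7.2 leaves open to exclusion. Protocol Sections 8.2.2 and 8.3.1 also omit the eligibility condition.

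Second, the SAP is transparent. The change is declared in Section 13; set sizes are tabulated and exclusion reasons listed (7.1); deviations are summarised and listed (7.2); and tumour responses are listed with a responder flag (8.1 and 8.2.2). This also stands, and a reader who inferred concealment would be wrong. The gap is one missing result.

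Third, response is derived by program, which limits discretion over the numerator. That is true, but the question here is who is counted.

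Fourth, the shifts are small against intervals 18 to 21 points wide. That is fair, and it is why the point is minor.

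Two stronger readings are tempting. One is that the rule will be used to raise the ORR. Nothing in the documents shows this, and in the illustration the downward shifts are the larger ones. The other is that stopping or expansion decisions are affected. They are not, because those rules count patients without this exclusion.

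**Conclusion.** The concern holds as a matter of opportunity. The exclusion is added by the SAP, has no objective criteria, is decided late in an open-label trial, and no final ORR is planned without it. Whether any exclusion would depend on response, and in which direction, cannot be known from the documents.

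The size rests on two assumptions: 1 to 4 exclusions, and all of them in one response class. On 13/48 that moves the ORR by between −6.6 and +2.5 points, and every value stays inside the base interval. On 8/35, upward shifts reach 2.9 points (25.81% − 22.86%). The extreme downward case (12.9%) falls just below the base interval's lower limit of 13.8%. Mixed or outcome-blind exclusions would shift the ORR less.

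This is a cheap improvement of minor severity. The word Safety in SAP Section 7.2 is simply wrong as written.

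**What to change.** - **Primary ORR set.** Use the protocol 8.3.1 set: measurable disease at baseline and at least one dose. Drop the SAP's randomisation condition so that the non-randomised arms B7 and B8 (protocol Section 3.5) stay in. Keep only the stated exclusion of manually assigned patients (protocol Sections 4.2.2 and 7.7.7; SAP Table 2).
- **Sensitivity analyses.** Report (a) ORR on the protocol 7.7.8 set, meaning all eligibility criteria met and, in combination arms, at least one combination dose; and (b) ORR on the deviation-excluded set, with one table giving each excluded patient's reason and response.
- **Arm B3.** Present it split as SAP Section 6.1.1 specifies, so that the 10 identified B3 patients count in the pooled first-line group and not in the second-line-plus estimate.
- **Wording.** Delete Safety from the exclusion sentence in SAP Section 7.2, and reconcile the OS-12 set between Table 3 and Section 8.3.9. The PK and pharmacodynamic exclusions may stay.

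The cost is SAP wording and one or two extra tables, with no new data. The primary ORR may move slightly in either direction.
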